## Overview of Planned Analyses

There will be a baseline analysis, 3 interim analyses, and a final analysis. Baseline and interim analyses are descriptive and for monitoring purposes. Multiplicity corrections will not be considered. Statistical analyses will be performed using the Electronic Case Report Form (eCRF) data gained until the cutoff dates described in the following subsections.

If the start of cladribine Year 2 treatment needs to be delayed (e.g., to allow for lymphocyte recovery to at least 800 cells/mL), all Year 2 visits and procedures will be moved out accordingly (at most 6 months). If recovery to 800 cells/mL is not complete after the 6-month delay, Year 2 treatment should not be initiated; the patient will nonetheless be followed up until the end of the observation period.

### 6.1

### First Interim Analysis

In the first interim analysis, safety, adherence, and PRO data will be analyzed for the subset of the first 30 patients enrolled in the study after they have completed the 6-month timepoint. This analysis will be conducted primarily for evaluation of safety.

All safety data (AEs) and hematology data, **CCI** status and lymphocyte subtype data (as available), will be evaluated descriptively. Treatment adherence will be evaluated on the basis of the modified versions of the MS-TAQ (at baseline modified for once- or twice-daily oral dosing to assess adherence during the last previous oral DMD treatment or modified to assess adherence during the last previous infused DMD treatment; at Month 1 and Month 2 modified for cladribine tablets). For each PRO score (TSQM [also called TSQM-1.4], SF-36, MFIS-5, BDI-FS, WPAI-MS, and PDDS), the actual value at each visit and change in scores from Baseline to Month 6 will be described.

### 6.2

### Baseline Interim Analysis

The baseline analysis will summarize the patient's baseline characteristics. It will be carried out when the baseline data collected on all patients are available.

Baseline characteristics of patients initiating cladribine tablets, including demographics, baseline PRO data, baseline laboratory data, baseline data on previous MS DMD use, relapses during the previous 2 years (or since MS diagnosis if diagnosis <24 months), baseline MRI data, and past treatment adherence, will be analyzed.

### **6.3                    Second Interim Analysis**

In the second interim analysis, safety, adherence, and PRO data will be analyzed as soon as 6-month data are available for all patients. This analysis will allow interim assessment of the safety of cladribine tablets in this study.

The same endpoints as the first interim analysis will be used.

### **6.4                    Third Interim Analysis**

The third interim analysis will be performed on the 12-month data for all patients.

This analysis will include all the endpoint analyses related to the objectives of the study. For the PROs, the actual value at each visit and the change in scores from Baseline to Months 6 and 12 will be considered. This analysis will allow interim assessment of all relevant aspects of the study.

### **6.5                    Final Analysis**

A final analysis will be performed on the 24-month data (or 30 months if Year 2 treatment is delayed) for all patients at the end of the study. The corresponding cutoff is expected by the end of March 2025.

The final analysis will include all the endpoint analyses related to the objectives of the study. For the PROs, the actual value at each visit and the change in scores from Baseline to Months 6, 12, and 24 will be considered. A comparison of the characteristics of patients who complete the study vs. those who drop out will be conducted as well.

## **7                    Changes to the Planned Analyses in the Clinical Study Protocol**

To account for the additional sub-cohort of patients who transition from ocrelizumab to cladribine and to account for the number of treated patients who are evaluable, the Precision of the 95% Confidence Interval (CI) for ARR has been updated.

CCI

The figure consists of a grid of horizontal bars. The top row contains several very long, thin black bars. Below this, a row is labeled 'CCI' on the left, with a very long bar extending across the row. The next section contains four groups of bars, each group with a label above it: 'CCII' (short bar), 'CCIII' (medium bar), 'CCIV' (medium bar), and 'CCV' (long bar). Below these are three more rows of bars, each with a label above it: 'CCVI' (long bar), 'CCVII' (medium bar), 'CCVIII' (medium bar), and 'CCIX' (long bar). The bottom section contains three rows of bars, each with a label above it: 'CCX' (long bar), 'CCXI' (medium bar), 'CCXII' (medium bar), and 'CCXIII' (long bar). The labels are in red text, and the bars are black.

## 8 Protocol Deviations and Analysis Populations

## 8.1 Definition of Protocol Deviations and Analysis Populations

Important protocol deviations are protocol deviations that might significantly affect the completeness, accuracy, and/or reliability of the study data or that might significantly affect a patient's rights, safety, or well-being.

Important protocol deviations include:

- Patients who are enrolled in the study despite not satisfying the inclusion/exclusion criteria
- Patients that no longer meet the inclusion/exclusion criteria while on the study but are not withdrawn (e.g., patients may have withdrawn consent)

The following deviations will be identified and confirmed prior to or at the Data Review Meeting, at the latest.

Important protocol deviations include:

- Deviations from the inclusion and exclusion criteria
- Deviations post-inclusion
  - The subset of these important protocol deviations that are clinically important, i.e., leading to the exclusion of a patient from an analysis population (see Section 8.2)

All important protocol deviations will be documented in Standard Data Tabulation Model datasets, whether identified through site monitoring, medical review, or programming.

## 8.2 Definition of Analysis Populations and Subgroups

### Full Analysis Set (FAS)

The FAS includes all patients enrolled in the study who have received at least 1 dose of cladribine tablets.

### Per-Protocol Analysis Set (PP)

The PP analysis set includes all patients who have completed a full treatment course of cladribine tablets (2 weeks of treatment [4-5 doses per week] for Years 1 and 2), according to the USPI, and are compliant with all entry criteria and without protocol deviations.

If the PP analysis population includes at least 90% of patients in the FAS analysis population, additional efficacy analyses on the Per-Protocol analysis population will be omitted, as differences in the results based upon these 2 analysis populations are expected to be negligible.

### Safety Analysis Set (SAF)

The SAF includes all patients enrolled in the study who have received at least 1 dose of cladribine tablets (same as FAS).

### Additional Subgroup Analysis Populations

Analyses	Analysis Population		
	Full Analysis Set	Per-Protocol Analysis Set	Safety Analysis Set*
Baseline assessments (baseline characteristics of patients initiating cladribine tablets, baseline PRO data, baseline laboratory data, baseline data on previous MS DMD use, relapses during the previous 2 years [or since MS diagnosis if diagnosis <24 months], baseline MRI data, retrospective MRI data, and past treatment adherence)	✓	✓	✓
Compliance and exposure	✓		✓
Primary endpoint analysis (ARR over the 24-month period)	✓	✓	✓

Analyses	Analysis Population		
	Full Analysis Set	Per-Protocol Analysis Set	Safety Analysis Set*
Secondary endpoints analysis: The ARR over the 12-month follow-up period, Sensitivity analyses of the ARR, ARR during the last 24 months (or since MS diagnosis if diagnosis <24 months) before starting cladribine tablets, Other relapse analyses	✓	✓	✓
Treatment patterns (MS treatment during the last 2 years (or since MS diagnosis if diagnosis <24 months) before transition to cladribine tablets, concomitant treatment for MS, follow-up treatment in case of discontinuation of cladribine tablets)	✓		✓
PROs and treatment adherence	✓		✓
Analyses of MRI imaging data	✓		✓
CCl [REDACTED]	CCl [REDACTED]		■
Analyses of ALC, as well as complete blood count and lymphocyte subsets, if available	✓	✓	✓
Concomitant medications	✓		✓
Safety	✓		✓

AE: adverse event; ALC: absolute lymphocyte count; ARR: annualized relapse rate; DMD: disease-modifying drug; FAS: Full Analysis Set; CCl [REDACTED]; MRI: magnetic resonance imaging; MS: multiple sclerosis;

PRO: patient-reported outcome.

\*Remark: Safety Analysis Set coincides with FAS for this study.

Subgroup analyses will be performed for the primary endpoint on subgroups, as defined below.

### Subgroups:

The following subgroups will be defined:

- Patients completing the 24-month study
- Patients not completing the 24-month study (i.e., lost to follow-up, withdrawing consent, protocol deviations)
- Patients not completing the treatment (i.e., completing Year 1 treatment but not Year 2 treatment, or not completing both courses of treatment each year)
- Type of MS at screening: RRMS, aSPMS, PPMS, CIS
- Patients diagnosed with MS <24 months before transitioning to cladribine tablets
- Centers
  - Pooling of centers: Because of the high number of participating centers and the anticipated small number of patients in each center, data will be pooled across centers,

and the factor centers will not be considered in statistical models or for subgroup analyses.

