- Treatment adherence questions, based on modified versions of the Multiple Sclerosis Treatment Adherence Questionnaire (MS-TAQ); data to be collected via ePRO at baseline (modified for once or twice daily oral dosing to assess adherence during last previous oral DMD treatment or modified for infusion dosing to assess adherence to last previous infusion DMD treatment) and at the end of Months 1, 2, 13, and 14 (modified for cladribine tablets); a Spanish translation is available to patients.
- Proportion of patients experiencing a relapse. For this study, a relapse will be defined as determined and recorded by the investigator and information on the definition used by the investigator will be collected (see Section 9.1.2.1 for a guide on definition).
- Proportion of patients with relapse associated with hospitalization (relapse as primary diagnosis or reason for hospitalization). For this study, a relapse will be defined as determined by the investigator (see Section 9.1.2.1 for a guide on definition).
- Proportion of patients with relapse associated with glucocorticoid use. For this study, a relapse will be defined as determined by the investigator (see Section 9.1.2.1 for a guide on definition).
- Assessment of previous treatment for MS:
 - Previous DMD(s) received for MS prior to study enrollment, since MS diagnosis
 - Reasons for discontinuation of previous DMD(s)
- Assessment of clinical and demographic characteristics of patients who switch from ocrelizumab to oral cladribine tablets
 - Reasons for discontinuation of ocrelizumab
- Proportion of patients who discontinue oral cladribine tablets
 - Reason for discontinuation of cladribine tablets
 - Elapsed time to discontinuation after first dose
 - Number of doses and % of planned doses (as per USPI) received
 - Subsequent treatment chosen following discontinuation of cladribine tablets
- Assessment of concomitant MS medications used during study period
- The ARR based on the last 24 months (or since MS diagnosis, if diagnosis <24 months) prior to the start of treatment with cladribine tablets (retrospective data). For this study, a relapse will be defined as determined by the investigator (see Section 9.1.2.1 for a guide on definition).

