9.9 Limitations of the Research Methods

As this study is being conducted as an observational study, data will be collected in the context of routine clinical care and standard of care rather than with a mandated clinical visit and assessment completion schedule. This may lead to inconsistent and variable data collection across patients and may result in missing data or information bias. In addition, variability in the treatments received may limit interpretation of the results. However, the objectives of this study are to assess real-world effectiveness, safety, and treatment patterns of cladribine tablets and therefore an observational design is the appropriate method to achieve the study objectives.

The patients enrolled in this study may not be generalizable to all patients in the US receiving cladribine tablets for RMS. This will be addressed by including a heterogeneous group of study sites that are broadly representative of MS care centers in the US.

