### **Significance Level**

When CIs are to be calculated, these will be two-sided, with a confidence probability of 95%, unless otherwise specified in this IAP. For continuous data, CIs for the mean will be calculated assuming a normal distribution of the data. CIs for binary endpoints will be presented using the Clopper-Pearson method. All statistical tests mentioned in this IAP are to be regarded as exploratory. The significance level is 5% two-sided. If p-values are to be presented for descriptive purposes, it will be indicated with the statement that no inferential conclusion should be drawn from the p-value.

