## **14                    Efficacy Analyses**

### **14.1                Primary Endpoint: ARR**

#### **14.1.1            Primary Objective: Analysis of the ARR**

Analysis (Analysis Population)	Derivation	Statistical Analysis Methods	Missing Data Handling
Primary endpoint: ARR over 24 Months			
Primary (FAS)	
ARR over 24 months. The ARR over 24 months of a patient is calculated as the number of relapses of the patient, divided by the number of days on study for that patient and multiplied by 365.25. This variable will be considered to get population estimates.
 
A relapse will be defined as per routine clinical practice, as determined by the Investigator.
 
Time on study (days) = (Date of study completion or date of study discontinuation - date of first dose of cladribine tablets + 1)
	
The population estimate will be based on the average of the ARR values for the patients in the study. The corresponding 95% CI will be reported. The Statistical Analysis System (SAS)® MEANS procedure will be used to compute these quantities. The following descriptive statistics will be reported: mean, SD, min, max, median, first quartile (Q1), and third quartile (Q3).
	
Patients discontinuing early are analyzed according to the number of years of follow-up on treatment and the number of relapses observed up to the time of discontinuation.

Secondary (PP)			

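### The primary ARR confidence interval treats patients as independent and the plan leaves centre out, so the interval may be somewhat too narrow if relapses cluster by site

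*SAP*

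**What the plan says.** SAP 8.2 (Subgroups, Centers) gives one reason for pooling: many centres are expected, with few patients in each. It concludes that "the factor centers will not be considered in statistical models or for subgroup analyses".

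The primary analysis in SAP 14.1.1 is a mean over patients: "The population estimate will be based on the average of the ARR values for the patients in the study". The interval comes from the same step, since the SAS "MEANS procedure will be used to compute these quantities". SAP 9 (Significance Level) says of confidence intervals that "these will be two-sided, with a confidence probability of 95" percent, and adds: "For continuous data, CIs for the mean will be calculated assuming a normal distribution of the data". The NB and zero-inflated NB models in SAP 14.1.1 and 14.1.2 have an offset for time on study and one covariate, the prior relapse category. The available text contains no random centre effect, no GEE and no cluster-robust variance.

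On the outcome, SAP 14.1.1 states: "A relapse will be defined as per routine clinical practice, as determined by the Investigator". Protocol 9.1.2.1 offers a guide (symptoms lasting at least a day, at least 30 days after the preceding attack, no fever or infection) but does not require it. Protocol 9.1.2.2 adds that "information on the definition used by the investigator will be collected". No analysis in the available text uses that record.

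**The concern.** Patients at one site share the clinicians who decide what counts as a relapse, and they share local visit and treatment habits. Protocol 9.2.4 leaves visit timing to routine care. These are ordinary reasons to expect some positive correlation between relapse counts within a site, and an interval built from SD/√n does not allow for it.

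The SAP's reason for leaving centre out does not settle the matter. Many small centres is a sound argument against fixed centre effects and against centre subgroups. It is not an argument against a variance that allows for clustering, because many small clusters is the setting in which a cluster-robust variance works well.

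At stake is the primary result. The study is single-arm and aims to estimate the ARR, so the 95% CI is its main statement of uncertainty about that number.

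**Working it through.** **What can be reproduced.** There is no figure in the plan to reproduce. SAP 7 says the precision of the ARR interval was updated, but the figures are redacted. The number of centres, patients per centre, ICC, expected ARR and SD are not visible. Everything below rests on assumed values for these.

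**Formulas.** With m patients per site (equal sizes):
- design effect DEFF = 1 + (m − 1) × ICC
- width of a clustered CI relative to the planned CI = √DEFF
- actual coverage of the nominal 95% CI = 2Φ(1.96/√DEFF) − 1

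Example, m = 5 and ICC = 0.10: DEFF = 1 + 4 × 0.10 = 1.40; √1.40 = 1.183; coverage = 2Φ(1.657) − 1 = 90.2%.

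| Patients per site | ICC | DEFF | Width factor | Coverage |
|---|---|---|---|---|
| 3 | 0.02 | 1.04 | 1.02 | 94.5% |
| 3 | 0.05 | 1.10 | 1.05 | 93.8% |
| 3 | 0.10 | 1.20 | 1.10 | 92.6% |
| 5 | 0.02 | 1.08 | 1.04 | 94.1% |
| 5 | 0.05 | 1.20 | 1.10 | 92.6% |
| 5 | 0.10 | 1.40 | 1.18 | 90.2% |
| 10 | 0.05 | 1.45 | 1.20 | 89.6% |

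With ICC = 0, or one patient per site, the factor is 1.00.

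**Uneven sites.** If site sizes have coefficient of variation cv, DEFF = 1 + ((1 + cv²)m − 1) × ICC. With cv = 0.7 and ICC = 0.05:
- m = 3: 1 + (4.47 − 1) × 0.05 = 1.17, width factor 1.08
- m = 5: 1 + (7.45 − 1) × 0.05 = 1.32, width factor 1.15
- m = 10: 1 + (14.9 − 1) × 0.05 = 1.70, width factor 1.30

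**Simulation check.** Gamma-Poisson counts over 2 years, with assumed ARR 0.2, dispersion 1, about 250 patients, a log-normal site effect and 4,000 runs (Monte Carlo error about 0.3 percentage points). Coverage of the planned type of interval:

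| Site log-SD (count-scale ICC) | m = 3 | m = 5 | m = 10 |
|---|---|---|---|
| 0 (0) | 94.5% | 94.5% | 94.8% |
| 0.3 (about 0.026) | 93.4% | 93.1% | 91.7% |
| 0.5 (about 0.07) | 93.0% | 90.6% | 86.5% |

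An interval built from site means covered 93.2% to 94.3% in the six settings with a site effect. The direction and rough size agree with the formula.

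**On the ARR scale.** With the same assumed ARR, dispersion and 250 patients, the SD of a patient's ARR is √(0.4 + 0.4²)/2 = 0.374, and the planned half-width is 1.96 × 0.374/√250 = 0.046. Clustering changes it to 0.047 (m = 3, ICC 0.02), 0.051 (m = 5, ICC 0.05) or 0.055 (m = 5, ICC 0.10: 0.0464 × 1.183).

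**The case against.** A reader might infer that the interval is too narrow as a matter of fact. The documents do not show that. It requires both a positive within-site correlation and several patients per site, and neither is visible.

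A reader might also take the large end of a wider grid as the likely size. An interval 30% too narrow, with coverage near 87%, needs 8 patients per site and an ICC of 0.10 together (DEFF = 1 + 7 × 0.10 = 1.70; √1.70 = 1.30). That sits poorly with the SAP's premise of few patients per centre. In the simulation, an ICC of only about 0.07 already implies a roughly 7-fold spread in relapse rate between sites at the 2.5th and 97.5th percentiles (exp(2 × 1.96 × 0.5) = 7.1).

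The evidence for a site effect has limits. The guide in Protocol 9.1.2.1 is a common anchor, though not a binding one. The phrase "including a heterogeneous group of study sites" in Protocol 9.9 belongs to a sentence about generalizability and is not evidence that sites judge relapse differently. Nothing says that each site has a single investigator with a distinct definition.

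Two further points are fair. First, the SAP sentence excludes centre as a factor, so it does not clearly forbid a cluster-robust variance, and striking its reference to models would not change an interval computed by PROC MEANS. Second, sites are targeted, not sampled at random. If inference were confined to the enrolled sites, between-site variation would not be sampling error. But Protocol 9.9 wants the sites to represent US MS care broadly, which points to inference beyond them.

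Finally, no decision rule or type I error depends on this: the study is estimation-only, and SAP 9 treats all tests as exploratory.

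These points limit the size and certainty of the concern. They do not remove it, because no planned analysis would show whether clustering matters.

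**Conclusion.** The concern holds in conditional form. The primary 95% CI for the mean ARR and the NB sensitivity intervals assume independent patients, centre is left out on grounds that argue only against fixed effects and subgroups, and the outcome is judged locally. If patients within a site are positively correlated, the intervals may be somewhat too narrow. For an assumed 3 to 5 patients per site and ICC 0.02 to 0.10, the understatement is about 2% to 18% of width, with coverage of about 94.5% down to 90%. At the low end this is trivial. It reaches 20% or more only with larger sites (about 10 patients at ICC 0.05) or a combination of higher ICC and very uneven enrolment. The point estimate does not change. A clustered interval beside the planned one is worth adding because it is cheap and bears on the study's primary output. The planned interval need not be replaced.

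**What to change.** 1. Keep pooling centres for the point estimate, and keep centre out as a fixed effect and as a subgroup.
2. Add to SAP 14.1.1 and 14.1.2 a site-clustered 95% CI for the FAS mean ARR (PROC SURVEYMEANS with CLUSTER site) and for the NB rate (GENMOD with REPEATED SUBJECT=site and an independence working correlation). Report both beside the planned intervals.
3. Report the distribution of patients per site. Protocol 6 records the last consent on 28 November 2022 and SAP 4.0 is dated 23 January 2025, so actual site sizes can replace the expectation in SAP 8.2.
4. Reword the Centers item in SAP 8.2 to say that centre is not used as a fixed effect or subgroup but is the cluster for these variances.
5. Do not apply the clustered variance to very small subgroups drawn from few sites. The treatment non-completer analysis in SAP 14.1.4 can run with just over 10 patients, where the many-clusters argument need not hold.

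The proposal does not cover the zero-inflated NB model or the multiple-imputation analysis, and the SAP should say so. The cost is a short text change, minor programming and probably a slightly wider interval; no new data are needed. If clustering is negligible, the two intervals will nearly coincide and the planned one is supported.

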**Sub-Cohort:**

The Ocrelizumab Sub-Cohort will consist of patients who transition from ocrelizumab to cladribine. Sub-cohort analyses will be performed for demographics (Section 11.1) and other baseline characteristics (Section 11.3), depending on the availability of data.

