Research question and objectives	
The main research questions are to evaluate the effectiveness and safety of cladribine tablets in patients with RMS, including RRMS and aSPMS, who transition to cladribine tablets after suboptimal response to any other oral DMDs or any infusion DMDs approved in the US for RMS in a real-world setting. Additionally, this study will separately describe real-world clinical and demographic characteristics that contribute to sequential treatment patterns among a sub-cohort of patients who transition from ocrelizumab to cladribine.
 
Primary Objective:
 
• To estimate the annualized relapse rate (ARR) over a 24-month period in patients with RMS, including RRMS and aSPMS, who are treated with cladribine tablets in a real-world setting and after suboptimal response to any other oral DMDs or any infusion DMDs approved in the US for RMS 
Secondary Objectives:
 
• To assess PROs, treatment adherence and treatment satisfaction during treatment with cladribine tablets• To assess treatment patterns (MS treatment prior to transition to cladribine tablets since MS diagnosis, concomitant treatment for MS during the last 2 years before transition to cladribine tablets (or since MS diagnosis, if diagnosis <24 months), follow-up treatment in case of discontinuation of cladribine tablets); and in particular, to assess the clinical and demographic characteristics related to the sequential use of ocrelizumab and cladribine• To estimate the ARR over the 24-month period prior to initiation of cladribine tablets (or since MS diagnosis, if diagnosis <24 months)• To collect all serious adverse events (SAEs), adverse drug reactions (ADRs), adverse events of special interest (AESIs) and special situations during and following treatment with cladribine tablets over a 24-month period

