Data about the safety and effectiveness of cladribine tablets in real-world clinical settings are still limited since cladribine tablets were approved for treatment of adult patients with highly active RMS in August 2017 in the European Union. The product has recently been approved by the FDA in the US. Real-world data are also limited about patients' adherence to treatment with cladribine tablets, patient-reported outcomes (PROs), and treatment patterns for RMS before, during, and after treatment with cladribine tablets in patients with suboptimal response to prior oral or infusion DMDs.

8 Research Question and Objectives

The main research objectives are to evaluate the effectiveness and safety of cladribine tablets in patients with RMS, including RRMS and aSPMS, who transition to cladribine tablets after suboptimal response to any other oral DMDs or any infusion DMDs approved in the US for RMS in a real-world setting. Additionally, this study will separately describe real-world clinical and demographic characteristics among a sub-cohort of patients who transition from ocrelizumab to cladribine.

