8.2 Secondary Objectives

- To assess PROs, treatment adherence and treatment satisfaction during treatment with cladribine tablets
- To assess treatment patterns (MS treatment prior to transition to cladribine tablets since MS diagnosis, concomitant treatment for MS during the last 2 years prior to initiation of cladribine tablets (or since MS diagnosis, if diagnosis <24 months), follow-up treatment in case of discontinuation of cladribine tablets); and in particular, to assess the clinical and demographic characteristics related to the sequential use of ocrelizumab and cladribine
- To estimate the ARR over the 24-month period prior to initiation of cladribine tablets (or since MS diagnosis, if diagnosis <24 months)
- To collect all serious adverse events (SAEs), adverse drug reactions (ADRs), adverse events of special interest (AESI) and special situations during and following treatment with cladribine tablets over a 24-month period

CCI

9 Research Methods

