9.2.2 Definition of Study Cohorts and Description of Treatments

The study will have a single primary cohort that consists of all patients enrolled in the study who received at least 1 dose of cladribine tablets. Additionally, a sub-cohort of approximately 100 patients that directly switched from ocrelizumab to cladribine tablets will be prospectively enrolled. All treatment and other medical decisions will be made by the investigator, with no directives mandated by this study protocol.

All study patients are anticipated to receive marketed cladribine tablets as per investigator discretion and as per US approved label: 3.5 mg/kg body weight over 2 years, administered as 1 treatment course of 1.75 mg/kg per year. Each treatment course consists of 2 treatment weeks, 1 at the beginning of the first month and 1 at the beginning of the second month of the respective year. Each treatment week consists of 4 or 5 days on which a patient receives 10 mg or 20 mg (1 or 2 tablets) as a single daily dose, depending on body weight. Since prescribing is determined by the investigator as per standard of care and according to the USPI, the benefits and risks to patients in being in the study are not different than the benefits and risks to patients taking cladribine tablets as per standard of care and according to the USPI in the general population.

Following completion of the 2 treatment courses, do not administer additional cladribine tablet treatment during the next 2 years, as stated in the USPI.

As per USPI, ALC values need to be normal at the initiation of cladribine tablets in Year 1, and ALC results need to indicate ≥ 800 cells per microliter at the start of the Year 2 treatment course. If necessary, the Year 2 treatment course should be delayed for up to 6 months to allow for recovery of lymphocytes to ≥ 800 cells per microliter. If this recovery takes more than 6 months, the patient should not receive further treatment with cladribine tablets.

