## **11                    Demographics and Other Baseline Characteristics**

If not stated otherwise, summaries will be presented for the FAS and PP populations. Missing values for the Baseline characteristics will be treated as described in Section 9, unless otherwise stated.

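### The ocrelizumab sub-cohort has no separate comparison group, so the planned tables cannot directly show which characteristics relate to the ocrelizumab-to-cladribine sequence

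*SAP*

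**What the plan says.** The protocol states the aim for the sub-cohort in three strengths.

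- Secondary objective (Protocol 8.2, repeated on the title page, in the abstract and in the SAP 5 objectives table): "to assess the clinical and demographic characteristics related to the sequential use of ocrelizumab and cladribine".
- Research question in the abstract (Protocol 4), which is stronger: "clinical and demographic characteristics that contribute to sequential treatment patterns among a sub-cohort of patients who transition from ocrelizumab to cladribine".
- Research question on the title page and in Protocol 8, which is purely descriptive: "this study will separately describe real-world clinical and demographic characteristics among a sub-cohort of patients who transition from ocrelizumab to cladribine".

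Protocol 9.2.2 defines a "single primary cohort that consists of all patients enrolled in the study who received at least 1 dose of cladribine tablets", and adds that "a sub-cohort of approximately 100 patients that directly switched from ocrelizumab to cladribine tablets will be prospectively enrolled". The listed outcome in Protocol 9.1.2.2 is an assessment of the characteristics of patients who make this switch, together with their reasons for stopping ocrelizumab.

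SAP 8.2 gives the analysis: "Sub-cohort analyses will be performed for demographics (Section 11.1) and other baseline characteristics (Section 11.3), depending on the availability of data". For baseline data generally, SAP 11 says that "summaries will be presented for the FAS and PP populations". The one planned comparison of characteristics between groups is in SAP 6.5: "A comparison of the characteristics of patients who complete the study vs. those who drop out will be conducted as well". Prior DMD is not among the subgroups in SAP 8.2, and those subgroups serve the primary endpoint.

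**The concern.** To say that a characteristic is related to a treatment sequence, some patients must have the sequence and some must not. Everyone in the sub-cohort made the same switch, so a table of that group alone gives the prevalence of each characteristic among switchers and no more.

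The nearest available contrast is the FAS column, but the FAS includes the sub-cohort. A comparison by eye pulls the two columns together, and the larger the sub-cohort's share of the FAS, the stronger the pull. The patients who came to cladribine from other drugs have the same baseline variables recorded (Protocol 9.3), but no demographic or clinical summary is planned for them as a group.

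At stake is a secondary objective for which about 100 patients were to be enrolled. The report would either say nothing on relatedness or rest it on an overlapping comparison that makes differences look smaller than they are.

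**Working it through.** **Is there a contrast anywhere?** Four places in the SAP could hold one.

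1. SAP 8.2, Sub-Cohort: summaries of demographics and other baseline characteristics, with no reference group.
2. SAP 8.2, Subgroups: study completion, treatment completion, MS type, recent diagnosis, centers. Prior DMD is absent.
3. SAP 11: FAS and PP columns. The FAS is all treated patients, so it contains the sub-cohort. The PP is drawn from treated patients and may also contain sub-cohort members.
4. SAP 6.5: completers against dropouts.

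None sets ocrelizumab switchers against a group that excludes them.

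**What the sub-cohort table alone gives.** A characteristic seen in 30 of 100 patients has an exact (Clopper-Pearson) 95% CI of 21.2% to 40.0%. That describes switchers and carries no information on association.

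**What the FAS column does to a difference.** The sub-cohort size of about 100 is from Protocol 9.2.2. The number of other treated patients, m, is not visible: the precision figures in SAP 7 are blacked out. I assume 100 to 200, with 50 and 300 as outer values. Protocol 6 records 150 patients consented by 30 November 2020, before the July 2021 amendment that added the sub-cohort. That makes the range plausible but does not fix it, since some of those 150 may themselves be ocrelizumab switchers.

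Write p_o for the proportion in the sub-cohort and p_x for the proportion in the others. Then

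FAS proportion = (100·p_o + m·p_x)/(100 + m)

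p_o − FAS proportion = [m/(100 + m)]·(p_o − p_x)

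The apparent difference is therefore understated by the fraction 100/(100 + m).

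The 95% CI half-width for the direct contrast (normal approximation) is

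1.96·√[p_o(1 − p_o)/100 + p_x(1 − p_x)/m]

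For a hypothetical characteristic with p_o = 40% and p_x = 25% (true difference 15 points):

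| m (assumed) | FAS shows | Sub-cohort minus FAS | Understated by | Half-width, direct contrast |
|---|---|---|---|---|
| 50 | 35.0% | 5.0 points | 67% | 15.4 points |
| 100 | 32.5% | 7.5 points | 50% | 12.8 points |
| 200 | 30.0% | 10.0 points | 33% | 11.3 points |
| 300 | 28.75% | 11.25 points | 25% | 10.8 points |

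Worked lines for the main range:

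- m = 100: (40 + 25)/200 = 32.5%; 1.96·√(0.0024 + 0.001875) = 0.128.
- m = 200: (40 + 50)/300 = 30.0%; 1.96·√(0.0024 + 0.0009375) = 0.113.

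For a continuous variable such as age, the half-width for a standardized mean difference is 1.96·√(1/100 + 1/m), or 0.28 at m = 100 and 0.24 at m = 200.

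**What even a clean contrast can show.** Inclusion criterion 7 (Protocol 9.2.1) requires that the decision to start cladribine came before enrollment. Patients who stayed on ocrelizumab, or left it for another drug, are not in the study. The comparison is between prior-ocrelizumab and prior-other-DMD patients, all of whom chose cladribine.

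**The case against.** The strongest reply is that the plan is descriptive and delivers what it lists. The title page, Protocol 8, the outcome in Protocol 9.1.2.2 and the endpoint in SAP 5 all ask for the characteristics of patients who made this switch, and SAP 8.2 provides them. The objective sits inside a treatment-patterns objective and can be read as asking only for a description of patients with this sequence. This stands in part. It does not remove the objective's own wording, which speaks of relation and is current text in both documents.

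Four stronger readings are tempting and go further than the documents allow.

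- A reader might infer that the study sets an objective to find what contributes to the switch and then fails to analyze it. That verb appears only in the abstract's research question, not in any listed objective or endpoint.
- A reader might infer that patients from other drugs are never shown separately. SAP 11.3 tabulates, for each DMD used in the last 2 years, the number of patients and the reasons for stopping. Past adherence is collected on separate oral and infusion questionnaires. These outputs do not contrast demographic or clinical characteristics, but they exist.
- A reader might infer that the FAS column makes the difference unrecoverable. Where both columns report counts or means, the complement follows by subtraction: in the m = 200 example, (90 − 40)/(300 − 100) = 25%. SDs can be recovered too. Medians, quartiles and ranges cannot, and no difference or interval would be printed.
- A reader might infer that the added column would reveal why patients leave ocrelizumab. It would not, given who is enrolled, and an unlabelled contrast could encourage that misreading.

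Table shells are not among the documents, so the exact column layout cannot be confirmed.

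**Conclusion.** The point holds as a cheap improvement. The secondary objective speaks of characteristics related to the sequence, and no visible analysis compares ocrelizumab switchers with a non-overlapping group.

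Its size depends on the unseen number of other treated patients. At 100 to 200, an eye comparison with the FAS hides half to a third of any true difference. A direct contrast with half-widths of about 13 to 11 points would be informative only for moderate to large differences. The 40% and 25% are illustrative.

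It would be wrong to conclude that the design could identify drivers of the switch if only it were analyzed differently. Part of the problem is inconsistent wording across the protocol, and the only contrast the data allow is between groups of patients who all chose cladribine.

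**What to change.** 1. In SAP 8.2, define a second group: FAS patients who did not switch from ocrelizumab. Base membership on the direct switch described in Protocol 9.2.2, so that the two groups together make up the FAS.
2. In SAP 11.1 and 11.3, place that group in a column beside the sub-cohort, with standardized differences or differences and 95% CIs, labelled descriptive and unadjusted. If CIs are used, name the method, because SAP 9 gives one only for single means and single proportions.
3. State with the tables that they show how ocrelizumab switchers differ from patients who switched to cladribine from other DMDs, and not what leads patients to leave ocrelizumab, because those who stayed on it or switched elsewhere are not enrolled.
4. Align the abstract's research question with the descriptive wording on the title page and in Protocol 8.

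If the column is declined, the wording of the secondary objective should also be reduced to describing patients who make the transition.

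The cost is one column in tables already planned, a footnote and a wording change. No new data are needed, since prior DMDs and baseline variables are collected for every patient. The downside is longer tables and unadjusted contrasts that could be over-read without the label.
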